3. DESCRIPTION OF DESIGN AND TRIAL POPULATION

3.1 OVERALL TRIAL DESIGN AND PLAN

This is a prospective, randomised, open label, blinded endpoint (PROBE), active comparator trial and the clinical endpoints are being adjudicated by an IAC in a blinded fashion.

This trial is designed to test the safety in NVAf patients that have undergone a successful PCI (elective or due to ACS) with stenting and were treatment naïve or were receiving oral anticoagulant treatment (either with warfarin, another VKA or other novel oral anticoagulant) before the procedure.

Patients will be consented and screened after undergoing a successful PCI. Randomisation will occur on local laboratory results taken at the screening visit or on standard of care local laboratory results taken within 7 days prior to screening; central laboratory samples must be taken at randomisation prior to first intake of study drug. Randomisation can occur up to 120 hours post PCI, however within 72 hours is preferable. Study drug should be administered between 6 hours after sheath removal and preferably within 72 hours post PCI, with haemostasis assured, however up to 120 hours post PCI is allowed.

Patients aged < 80 years will be randomly assigned to 110mg dabigatran etexilate b.i.d., 150mg dabigatran etexilate b.i.d. or warfarin in a 1:1:1 ratio for the duration of the trial.

Patients aged ≥ 80 years will be randomly assigned depending on their geographical location:

- Patients aged ≥ 80 years in the USA will be assigned to 110mg dabigatran etexilate b.i.d., 150mg dabigatran etexilate b.i.d. or warfarin in a 1:1:1 ratio
- All other patients aged ≥ 80 years outside of the USA will be assigned to 110mg dabigatran etexilate or warfarin in a 1:1 ratio.

In addition to their randomised treatment:

- All patients will receive either clopidogrel (75mg q.d.) or ticagrelor (90mg b.i.d), according to the local label, for at least 12 months after randomisation. Discontinuation of clopidogrel or ticagrelor or switching to ASA (≤ 100 mg q.d.) after 12 months of treatment is at the discretion of the Investigator
- Patients randomised to receive warfarin will receive ASA (≤ 100 mg q.d.) for either one month in patients with a bare metal stent BMS and for three months in patients with a DES.

For details of drug administration see [Section 4.1.4](#).

The study plan is detailed in [Figure 3.1: 1](#).

Proprietary confidential information.

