4.1.4 Drug assignment and administration of doses for each patient

Each patient will be randomised at Visit 2 to receive either dabigatran etexilate (110mg or 150mg b.i.d.) or warfarin. The first dose of trial medication will be taken, between 6 hours after sheath removal and preferably within 72 hours post PCI, with haemostasis assured, however up to 120 hours post PCI is allowed.

Patient randomised to receive dabigatran etexilate:

It is permitted for patients to receive bridging therapy with a parenteral anticoagulant according to local practice before switching to dabigatran etexilate. Dabigatran etexilate should be given 0-2 hours prior to the time that the next dose of parenteral anticoagulant would be due, or at the time of discontinuation in case of continuous treatment (e.g. intravenous (i.v.) unfractionated heparin (UFH)). See [Appendix 10.1](#) for guidance how to switch from an anticoagulant to dabigatran etexilate.

Dabigatran etexilate capsules should be taken in the morning and in the evening (one at each timepoint), at the same time every day with a full glass of water. The capsules must not be crushed, nor opened and can be taken with or without food. If dyspeptic symptoms occur, the Investigator should consider adding a proton pump-inhibitor (PPI) or H2-blocker to the concomitant therapy of the patients.

The interval between doses should be as close to 12 hours as possible.

If a dose of dabigatran etexilate is missed for any reason, the forgotten dose may still be taken up to six hours prior to the next scheduled dose. From six hours prior to the next scheduled

Proprietary confidential information.

© 2016 Boehringer Ingelheim International GmbH or one or more of its affiliated companies. All rights reserved.

This document may not - in full or in part - be passed on, reproduced, published or otherwise used without prior written permission.

dose on, the “missed” dose should be omitted. A double dose to make up for missed individual doses must not be taken.

Any patient that decides to discontinue study medication should be considered for a switch to an appropriate (non-study) anticoagulant according to local practice. For patients receiving dabigatran etexilate, continuation of study drug for 2-3 days to assist bridging may be appropriate. For recommendations on how to switch from dabigatran etexilate to other anticoagulants see [Appendix 10.2](#)).

Patient randomised to receive warfarin:

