6.2.2 Treatment period(s)

All tests for the visits in the treatment phase are detailed in the Flow Chart.

After eligibility has been confirmed and all Visit 1 procedures done, Visit 2 can be conducted including randomisation via IRT. Screening and randomisation can be on the same day, depending on the availability of the screening laboratory results.

Randomisation can occur immediately after successful screening and up to 120 hours post PCI, however, randomisation within 72 hours is preferable. The first dose of trial medication

Proprietary confidential information.

© 2016 Boehringer Ingelheim International GmbH or one or more of its affiliated companies. All rights reserved.

This document may not - in full or in part - be passed on, reproduced, published or otherwise used without prior written permission.

will be taken between 6 hours after sheath removal and preferably within 72 hours post PCI (end of intervention i.e. when the last catheter used for PCI is removed), with haemostasis assured, however randomisation up to 120 hours post PCI is allowed.

Treatment visits will take place approximately every three months for the first 12 months of treatment and every six months thereafter. After month 12, phone calls will be conducted in between regular clinic visits. These calls are designed to encourage accurate and timely event reporting and continued engagement of patients.

As this is an OE driven trial, patients will remain in the treatment period until the necessary number of OEs is reached. Permanent study drug discontinuation is only justified when clear, persistent contraindications arise or when the patient requests to be withdrawn from study drug, see [Section 3.3.4.1](#).

All patients who discontinue treatment must be followed up until the end of the study. Patients who discontinue treatment must continue to be followed up according to the visit schedule until the end of the study. At these visits (as indicated in the [Flow Chart](#)) ECGs will be performed and the collection of AEs, OEs (including completion of the bleeding questionnaire) and use of concomitant medication will be made.

Patients that are not actively taking study drug may be less motivated to adhere to the study visit schedule. Investigator and site staff should work to detect early signs of losing interest and readily present such patients (not actively taking study drug) with the following opportunities to encourage continued participation:

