10. APPENDICES

APPENDIX 10.1 STUDY DRUG START AND BRIDGING RULES

10.1.1 When to start dabigatran etexilate following treatment by other anticoagulants

Heparins

UFH or LMWH/injectable anticoagulant (if given) should be stopped prior to the first dose of dabigatran etexilate. Dabigatran etexilate should be initiated with the following suggested time windows:

- UFH/other continuous i.v. anticoagulants: initiate dabigatran etexilate at the time the UFH/other continuous i.v. anticoagulant is stopped
- LMWH/other s.c. injectable anticoagulants: initiate dabigatran etexilate 0-2 hours prior to the time that the next dose of the LMWH/other s.c. injectable anticoagulant would be due.

Vitamin K antagonists

Patients already on VKA, should start dabigatran etexilate once the INR is <2.0 . If the INR is ≥ 2.0 , study medication can be dispensed but the patient will be instructed not to start it until notified. Follow-up INR testing will be performed in 1-2 day intervals until INR falls below 2.0, at which time the patient will be instructed to start taking the study medication.

Novel Oral Anticoagulants

Patients taking apixaban, edoxaban, rivaroxaban or dabigatran etexilate can be initiated at the time the next dose of the novel oral anticoagulant would have been due. As there is no clinical experience for switching from other novel oral anticoagulants to dabigatran etexilate, the decision must be taken based on clinical considerations and recommendations [P13-06400].

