A2.23	Patients not willing or able to comply with the protocol requirements or considered unreliable by the Investigator concerning the requirements for follow-up during the study and/or compliance with study drug administration, who have a life expectancy less than the expected duration of the trial due to concomitant disease, or who have any condition which in the opinion of the Investigator, would not allow safe participation in the study (e.g. drug addiction, alcohol abuse).	Exclusion criterion 23 met	PPS

Table 6.2: 1 (continued) Important protocol violations

Category/ Code	Description	Example/Comment	Excluded from
B	Informed consent		
B1	Informed consent not given	Inclusion Criterion 4	All
B2	Informed consent given too late or the dates of the investigator's and patient's signatures do not match		None
B3	Informed consent withdrawn	Only applies from the date at which consent is withdrawn.	All
C	Trial medication and randomization		
C1	Incorrect trial medication taken	Medication kit assigned not matching treatment patient was randomised to (e.g. patient randomized to warfarin-TAT but received 110mg DE-DAT)	PPS
C2	Randomisation order not followed	e.g. forced randomization, mis-stratification	PPS
C3	Non-compliance	
Compliance <80% or >120% over the course of the study for dabigatran patients (determined on a visit-wise basis), or time in therapeutic target range for warfarin patients <45% (also on a visit-wise basis). See Section 7.3 for details on compliance calculations. Patients will be flagged if they exhibit non-compliance for two consecutive visits or more (for both dabigatran and warfarin patients).
 
Non-compliance caused by temporary interruption of treatment due to a procedure or a drop in CrCl to less than 30mL/min should not be classified as a protocol violation.
	PPS, but only from start of non-compliance onwards
C4	Trial medication taken at the wrong time	First dose of study drug not administered at the correct time (should be between 6 hours after sheath removal and up to 120 hours post PCI)	PPS
D	Concomitant medication		

Table 6.2: 1 (continued) Important protocol violations

Category/ Code	Description	Example/Comment	Excluded from

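### First-dose timing rules conflict, so SAP violation C4 can drop some prior-VKA dabigatran patients from the per-protocol set for following Appendix 10.1.1

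*SAP*

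**What the plan says.** **SAP, Section 6.2, Table 6.2:1.** C4 flags the following: "First dose of study drug not administered at the correct time". The window is "should be between 6 hours after sheath removal and up to 120 hours post PCI", and the consequence is exclusion from the PPS. The row is not restricted to any arm and lists no exceptions. Two other rows matter:
- C3 (non-compliance) writes out its exemptions: interruptions for a procedure or for a fall in creatinine clearance below 30 mL/min are not violations.
- D2.1 (prohibited medication) four times sets aside washout or titration at study start and refers the reader to C4.

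**Protocol, limit on the first dose.** Flow chart footnote 17 and Sections 3.1 and 4.1.4 prefer dosing within 72 hours and add, as Section 4.1.4 puts it, "however up to 120 hours post PCI is allowed".

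**Protocol, limit on randomisation.** Section 3.1: "Randomisation can occur up to 120 hours post PCI, however within 72 hours is preferable". Section 6.2.2 gives the first-dose window but ends it with "however randomisation up to 120 hours post PCI is allowed", so there the 120 hours belongs to randomisation.

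**Protocol, switching from a VKA.** Under Appendix 10.1.1, patients already on a VKA "should start dabigatran etexilate once the INR is <2.0". If INR is 2.0 or higher, "study medication can be dispensed but the patient will be instructed not to start it until notified". The appendix adds: "Follow-up INR testing will be performed in 1-2 day intervals until INR falls below 2.0". No maximum wait is given. Flow chart footnote 15, however, confines follow-up INRs to patients randomised to warfarin.

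**The concern.** A dabigatran patient who was on a VKA and has INR 2.0 or above is told to wait. If the wait runs past 120 hours, C4 takes that patient out of the PPS for having waited. Appendix 10.1.2 states no INR threshold for starting warfarin, so a comparable patient in the warfarin arm meets no such written delay. Among patients following a written switching instruction, PPS membership then depends partly on assigned arm, prior VKA use and INR level.

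The PPS is a named robustness check on the primary non-inferiority comparison. Selective removal of higher-INR, prior-VKA patients from the dabigatran arms weakens the balance that makes the check useful. Sites also face first-dose instructions that cannot all be followed.

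**Working it through.** The plan states no figure on this point, so there is none to reproduce. The check is a comparison of passages plus timing arithmetic.

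**Inputs**
- First-dose limit: 120 h post PCI (SAP C4; protocol footnote 17, Sections 3.1 and 4.1.4).
- Latest randomisation: 120 h post PCI (protocol Sections 3.1 and 6.2.2).
- Retest interval: 1 to 2 days, i.e. 24 to 48 h (Appendix 10.1.1).
- Baseline INR: taken in all patients at the randomisation visit (flow chart and footnote 15).

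**Assumptions.** The retest clock starts at randomisation, and the first dose is given as soon as a retest shows INR below 2.0.

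**Formula.** For a patient with INR 2.0 or above, randomised R hours after PCI and qualifying at retest k, the first dose falls between R + 24k and R + 48k hours.

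| R (h) | k = 1 | k = 2 | k = 3 |
|---|---|---|---|
| 24 | 48–72, inside | 72–120, inside | 96–168, may be late |
| 48 | 72–96, inside | 96–144, may be late | 120–192, may be late |
| 72 | 96–120, inside | 120–168, may be late | 144–216, always late |
| 96 | 120–144, may be late | 144–192, always late | 168–240, always late |
| 120 | 144–168, always late | 168–216, always late | 192–264, always late |

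**Unavoidable conflict.** Even the quickest case (k = 1, 24 h) is late when R + 24 > 120, that is R > 96 h. Patients randomised earlier are late only if INR takes long enough to fall.

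**Arm comparison.** Under Appendix 10.1.2:
- warfarin may start alongside a parenteral anticoagulant;
- a switch from another VKA follows a nomogram in the site file, which is not among the documents;
- a prior NOAC is replaced by parenteral bridging while warfarin is initiated.

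No INR wait is stated in any of the three.

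**Scale.** The documents give neither the share of prior VKA users nor the share with INR 2.0 or above at randomisation, so no count can be derived. SAP Section 6.3 lets the PPS analyses be dropped if fewer than 10% of the treated set are excluded. Assuming a treated set equal to the planned 2502, that is 0.10 × 2502 ≈ 250 patients. If C4 delays in the dabigatran arms were the only exclusions, it would take 250 / (2 × 834) = 250 / 1668 ≈ 15% of planned dabigatran patients to reach it.

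**The case against.** The strongest reply is that C4 copies the protocol faithfully. Footnote 17 and Sections 3.1 and 4.1.4 all cap the first dose at 120 hours, so a later dose breaches them whatever the reason. This stands in part. A reader might infer that fully protocol-compliant patients are excluded; the documents do not support that. These patients follow Appendix 10.1.1 but break the cap elsewhere, and the contradiction starts inside the protocol. Section 4.1.4 itself sends sites to Appendix 10.1 for switching to dabigatran, though, so the appendix is part of the dosing instruction and C4 takes one side without saying so.

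A reader might also infer that C4 excludes dabigatran patients only. It does not: a warfarin patient dosed after 120 hours is excluded too. The supportable statement is that the available documents write an INR-directed delay only for dabigatran. The nomogram for VKA-to-warfarin switches cannot be checked.

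Third, the group is limited. Randomisation within 72 hours is preferred, and at 72 hours one satisfactory retest keeps the patient inside the window. This stands.

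Fourth, SAP Section 6.3 leaves final set membership to a meeting before database lock, blinded where possible, which could rescue such cases. It gives no rule for doing so. D2.1's references to C4 show that washout was foreseen, but the text they point to is absent.

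**Conclusion.** The point holds as a minor inconsistency with a limited analytic consequence. The protocol's first-dose rules contradict one another. C4 adopts the 120-hour cap with no washout exception, so some dabigatran patients with prior VKA use and INR 2.0 or above leave the PPS for following Appendix 10.1.1. For those randomised after 96 hours this is unavoidable, given 24 to 48 hour retests counted from randomisation. For others it depends on how fast INR falls.

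The number affected is unknown. The effect is confined to the PPS: one sensitivity analysis of the primary endpoint, which may not be run at all, and the PPS baseline tables. A reader might infer that the primary result or the testing hierarchy is at risk. The documents do not support that: the primary analysis uses the FAS, counted from randomisation, and the treated-set on-treatment analysis keeps these patients. Nor do they allow the size or direction of any bias in the PPS hazard ratio to be stated.

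**What to change.** 1. **Protocol.** Reconcile footnotes 15 and 17, Sections 3.1, 4.1.4 and 6.2.2, and Appendix 10.1.1 on when the first dose may be given and whether follow-up INRs are taken in these dabigatran patients. No view is offered here on which clinical rule is right.
2. **SAP C4.** Write in the washout provision to which D2.1 refers, parallel to the C3 exemptions: a late first dose in a dabigatran patient with prior VKA use and baseline INR 2.0 or above does not lead to PPS exclusion. Alternatively, report the PPS analysis with and without these patients and give their number by arm.

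The SAP cost is one table row or one extra analysis. Most of the data are already planned: baseline INR in all patients (footnote 15), VKA use from 30 days before consent (protocol Section 4.2), and date and time of first intake (SAP Section 6.1). The drawback is precision. These items identify INR-directed delays only approximately, because they do not show when INR fell below 2.0. An exact classification would need follow-up INRs recorded in these patients, which footnote 15 as written does not provide for.

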6.3 PATIENT SETS ANALYSED

The following analysis sets will be defined for this trial:

- **SCR – Screened Set**
All patients who signed informed consent and completed at least some screening procedures.
- **FAS – Full Analysis Set**
All consenting patients randomised will be analysed in the treatment group to which they are randomised regardless of whether they took study medication. The start date of the observation period for this analysis set is the date of randomisation. This follows the intent-to-treat principle. All patient listings will be based on the FAS except where specified otherwise. Refer to the technical TSAP for more detail.
- **TS – Treated Set**
The set of patients who receive at least one dose of study medication will be analysed according to the treatment they have received. The start date of the observation period for this analysis set is the date of first intake of trial medication.

- PPS – Per-Protocol Set
Patients will be included in the PPS, if they are already included in the TS and if they adhere to the trial protocol without any IPVs. IPVs are defined in [Section 6.2](#).

For rules on censoring, refer to [Section 7.4](#).

The final decision as to whether a patient is included in or excluded from each analysis set will be taken before database lock in a blinded manner, where possible and will be documented in the minutes of the RPM or Database Lock Meeting (DBLM). Some decisions may need to be taken after DBL (e.g. treatment switching). If the number of patients excluded from the PPS is small (<10% of the TS), then analyses on this set may not be conducted. This decision will also be documented in the minutes of the RPM or DBLM.

The following table identifies which patient set is used for which category of endpoints.

[figure not shown]
Table 6.3: 1 Patient sets analysed

[figure not shown]
Class of endpoint	Patient set		
	FAS*	TS	PPS#
Primary endpoint (see Section 5.1)	X	X	X
Secondary endpoints (see Section 5.2.2)	X	X	
Further endpoints (see Section 5.3)	X	X	
Safety endpoints other than the primary endpoint (see Section 7.8)	X	X	
Other safety endpoints (see Section 7.8.5)	X	X	
Demographic/baseline endpoints (see Section 7.1)	X		X

[figure not shown]
Note that the number of patients with available data for an endpoint may differ. For details, see [Section 6.6](#).

* The FAS will be the main analysis set for the summary of clinical outcome event data. Other analysis sets will be used for sensitivity purposes.

If the number of patients excluded from the PPS is small (<10% of the TS), then analyses on this set may not be conducted

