6.2 IMPORTANT PROTOCOL VIOLATIONS

The following table defines the different categories of Important Protocol Violations (IPVs). The final column describes which IPVs will be used to exclude patients from the different patient analysis sets. In this study, patients are either excluded from “All” analysis sets, the Per Protocol analysis Set (PPS), the Full Analysis Set (FAS) or “None” of the analysis sets. Refer to [Section 6.3](#) for more details. Most IPVs will be identified by the trial team prior to DBL, where possible in a blinded manner. Some programmatically-identified IPVs (e.g. treatment switching) will need to be identified after DBL.

Table 6.2: 1 Important protocol violations

Category/ Code	Description	Example/Comment	Excluded from
A	Entrance criteria not met		
A1.1	Male or female patients aged ≥ 18 years or ≥ 20 years in Japan.	Inclusion criterion 1 not met	PPS
A1.2	Patients with NVAf that have been receiving oral anticoagulant (OAC) treatment (either with warfarin, another Vitamin K Antagonist (VKA) or other novel oral anticoagulant), or were treatment naïve prior to PCI. Atrial Fibrillation (AF) may be paroxysmal, persistent or permanent, but must not be secondary to a reversible disorder such as MI, pulmonary embolism, recent surgery, pericarditis or thyrotoxicosis	Inclusion criterion 2 not met	PPS
A1.3	Patients presenting with: 
 • An Acute Coronary Syndrome (ACS) [ST elevation MI (STEMI), NSTEMI or unstable angina (UA)] that was successfully treated by PCI and stenting [either Bare Metal Stent (BMS) or Drug Eluting Stent (DES)] Or • Stable Coronary Artery Disease (CAD) with at least one lesion eligible for PCI that was successfully treated by elective PCI and stenting (either BMS or DES) 	Inclusion criterion 3 not met	PPS
A2.1	Patients with a mechanical or biological heart valve prosthesis	Exclusion criterion 1 met	PPS
A2.2	Cardiogenic shock during current hospitalisation	Exclusion criterion 2 met	PPS
A2.3	Patients who have used fibrinolytic agents within 24 hours of randomisation that, in the opinion of the Investigator, will put the patient at high risk of bleeding	Exclusion criterion 3 met	PPS
A2.4	Stroke within 1 month prior to screening visit (Additionally in Japan: a haemorrhagic stroke, 6 months prior to administration of study treatment)	Exclusion criterion 4 met	PPS

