A2.5	Patients, who in the opinion of the Investigator, have had major surgery within the month prior to screening	Exclusion criterion 5 met. Nature and timing of surgery to be reviewed at Report Planning Meeting (RPM).	None
A2.6	Patient has received an organ transplant or is on a waiting list for an organ transplant	Exclusion criterion 6 met	PPS
A2.7	History of intraocular, spinal, retroperitoneal or a traumatic intra-articular bleeding unless the causative factor has been permanently eliminated or repaired (e.g. by surgery)	Exclusion criterion 7 met	PPS

Table 6.2: 1 (continued) Important protocol violations

Category/ Code	Description	Example/Comment	Excluded from
A2.8	Gastrointestinal (GI) haemorrhage within one month prior to screening, unless, in the opinion of the Investigator, the cause has been permanently eliminated (e.g. by surgery)	Exclusion criterion 8 met	PPS
A2.9	Major bleeding episode (reduction in the haemoglobin level of at least 2g/dL, transfusion of at least two units ¹ of blood, or symptomatic bleeding in a critical area or organ) including life-threatening bleeding episode (symptomatic intracranial bleeding, bleeding with a decrease in the haemoglobin level of at least 5g/dL or bleeding requiring transfusion of at least 4 units ² of blood or inotropic agents or necessitating surgery) in one month prior to screening visit	Exclusion criterion 9 met	PPS
A2.10	Haemorrhagic disorder or bleeding diathesis (e.g. von Willebrand disease, haemophilia A or B or other hereditary bleeding disorder, history of spontaneous intra-articular bleeding, history of prolonged bleeding after surgery/intervention)	Exclusion criterion 10 met	PPS
A2.11	Anaemia (haemoglobin <10g/dL) or thrombocytopenia including heparin-induced thrombocytopenia (platelet count <100 × 10 ⁹ /L) at screening (Visit 1)	Exclusion criterion 11 met	PPS
A2.12	Severe renal impairment (estimated CrCl calculated by Cockcroft-Gault equation) <30mL/min at screening (Visit 1)	Exclusion criterion 12 met	PPS
A2.13	Active liver disease as indicated by at least one of the following: 
 • Prior and persistent alanine aminotransferase (ALT) or Aspartate transaminase (AST) or alkaline phosphatase (AP) >3 × upper limit of normal (ULN) • Known active hepatitis C • Known active hepatitis B • Known active hepatitis A 	Exclusion criterion 13 met	PPS

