A2.14	Recent malignancy or radiation therapy (≤6 months) unless, in the opinion of the Investigator, the estimated life expectancy is greater than 36 months	Exclusion criterion 14 met	PPS
A2.15	Need for continued treatment with systemic ketoconazole, itraconazole, posaconazole, cyclosporine, tacrolimus, dronedarone, rifampicin, phenytoin, carbamazepine or St. John's Wort.	Exclusion criterion 15 met	PPS

¹ Equivalent to 4.5 units in Japan

² Equivalent to 9 units in Japan

Table 6.2: 1 (continued) Important protocol violations

Category/ Code	Description	Example/Comment	Excluded from
A2.16	Patients who, in the Investigator's opinion, need continuous treatment with Non-Steroidal Anti-Inflammatory Drugs (NSAIDs)	Exclusion criterion 16 met	PPS
A2.17	Patients with a known allergy to dabigatran etexilate or to the excipients used for the capsule of the drug	Exclusion criterion 17 met	PPS
A2.18	Patients with a known allergy to warfarin tablets or to the excipients	Exclusion criterion 18 met	PPS
A2.19	Patients who, in the Investigator's opinion, should not be treated with OAC	Exclusion criterion 19 met	PPS
A2.20	Patients with a contraindication to clopidogrel, ticagrelor or aspirin (ASA)	Exclusion criterion 20 met	PPS
A2.21	Pre-menopausal women (last menstruation \leq 1 year prior to screening) who: 
 • Are pregnant or breast feeding or • Are not surgically sterile or • Are of child bearing potential and not practising two acceptable methods of birth control, or do not plan to continue practising an acceptable method of birth control throughout the trial. Acceptable methods of birth control are oral or parenteral (patch, injection, implant) hormonal contraception which has been used continuously for at least one month prior to the first dose of study medication, intrauterine device or intrauterine system, double-barrier method of contraception (condom and occlusive cap or condom and spermicidal agent), male sterilisation and complete sexual abstinence (if acceptable by local authorities). Periodic abstinence is not an acceptable method of contraception. 	Exclusion criterion 21 met. Pregnant patients will be excluded from the PPS.	None
A2.22	Patients who have participated in another trial with an investigational drug or device within the past 30 days preceding the screening visit or are participating in another trial (patients participating in an observational study only will not be excluded)	Exclusion criterion 22 met	PPS

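### SAP 6.3 defines the per-protocol set as patients with no important protocol violation at all, which contradicts SAP 6.2 and Table 6.2:1, and SAP 7.4 gives no censoring date for the partial exclusions

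*SAP*

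**What the plan says.** SAP 6.3 admits a patient to the PPS "if they are already included in the TS and if they adhere to the trial protocol without any IPVs", and says that IPVs are defined in 6.2.

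SAP 6.2 introduces Table 6.2:1 with: "The final column describes which IPVs will be used to exclude patients from the different patient analysis sets". It allows for IPVs that exclude from no set, and three rows are marked that way: A2.5 (recent major surgery), A2.21 (the criterion for pre-menopausal women) and B2 (late consent or mismatched signature dates). Three other rows are time-limited: C3 (study-drug compliance), D3.1 (aspirin) and D3.2 (clopidogrel or ticagrelor) carry "PPS, but only from start of non-compliance onwards". B3 (consent withdrawn) excludes from all sets, but its comment limits this to the time from withdrawal onwards.

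SAP 7.4 uses the TS and the PPS for the on-treatment robustness analysis of the primary endpoint. The main analysis is on the FAS. SAP 6.3 also has a skip rule: "If the number of patients excluded from the PPS is small (<10% of the TS), then analyses on this set may not be conducted".

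**The concern.** The two sections give different PPS patients, follow-up and events. A patient whose only IPV is B2 is out under 6.3 and fully in under the table. A patient with a single No for clopidogrel or ticagrelor at month 6 loses all follow-up under 6.3, but contributes up to the violation under the table.

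The second case can involve the endpoint itself. Under protocol 5.2.2.1, a bleed counts as clinically relevant non-major if, for example, it leads to medical treatment or to interruption of study drug. If the same bleed also leads to aspirin or the P2Y12 inhibitor being stopped, one visit ticked No raises D3.1 or D3.2. Rule 6.3 then removes the patient together with the bleed, so a primary event is deleted because of what followed it. Aspirin is mandated only in the warfarin arm (protocol 3.1 and 4.1.1), so D3.1 deletions can fall on one arm only. What is at stake is how to read one of the two robustness analyses behind the non-inferiority tests in Steps 1 and 2.

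**Working it through.** **1. The two rules side by side**

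| IPV | SAP 6.3 | Table 6.2:1, last column |
|---|---|---|
| A2.5, A2.21, B2 | patient out | patient in, all follow-up |
| C3, D3.1, D3.2 | patient out | in until non-compliance starts |
| B3 | patient out | out of all sets, from withdrawal onwards (comment) |
| Other rows marked PPS | patient out | patient out |

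**2. Which rule is meant.** SAP 6.2 gives the decision to the last column but refers to 6.3 for more detail, and 6.3 refers back to 6.2. SAP 7 plans to tabulate IPVs that exclude from the PPS separately from those that do not. Under 6.3 read literally the second group would be empty, so the table is the likelier intention.

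**3. Can the table be run?** For censoring, 6.3 points to 7.4. There, the on-treatment rule censors premature stoppers at last intake plus 6 days and has nothing for the start of non-compliance. The date is not obvious. C3 needs two consecutive non-compliant visits, and D3 is a visit-level tick box. If the start were set at the visit before the No, a bleed in that interval would be lost under the table's rule too.

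**4. A2.21 is also inconsistent within its row.** The last column excludes from no set, but the comment reads "Pregnant patients will be excluded from the PPS".

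**5. Design figures (protocol 7.6), to confirm that they are not at issue.** Power with 334 events, margin 1.38, one-sided 0.025 and true HR 1 (assumed): Φ(½·√334·ln 1.38 − 1.96) = Φ(0.983) = 83.7%, against 83.6% stated. With rate −ln 0.86 = 0.151 per year and follow-up uniform over 0.5 to 2.5 years, P(event) = 0.199 and 167/0.199 = 837 per arm, against 834 stated.

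**6. Sensitivity of the upper bound (illustration).** Start from 167 events in 834 patients per arm: HR 1.00, upper bound exp(1.96·√(2/167)) = 1.239. Remove k warfarin patients whose bleed preceded a violation: HR = (167/834) / ((167−k)/(834−k)), with SE √(1/167 + 1/(167−k)).
- k = 10: HR 1.051, upper bound 1.307.
- k = 20: HR 1.109, upper bound 1.384.
- 20 removed from each arm: HR 1.00, upper bound 1.257.

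**7. Simulation (assumed rates; the documents give none).** True HR 1, 834 per arm, 14% at one year, follow-up 6 to 30 months, and a background C3/D3 hazard of 0.15 per year in year 1. A first-year bleed is followed by a D3 violation with probability q, always after the bleed. Rate ratios, 800 replicates:
- Table rule: 0.99 to 1.01 throughout.
- Rule 6.3, q = 0.3 warfarin / 0.1 dabigatran over the whole first year: 1.15 to 1.17 between runs. Warfarin events fall from about 151 to 116.
- Rule 6.3, q = 0.2 / 0.1: 1.06 to 1.07.
- Rule 6.3, q = 0.1 / 0.3: 0.87.
- Rule 6.3, equal q of 0.1, 0.2 or 0.3: 0.99 to 1.01.
- Rule 6.3, the 0.3 / 0.1 difference confined to three months: 1.04 to 1.05; to one month: about 1.01.

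At the 0.15 background hazard, rule 6.3 removes 14 to 17% of patients outright. At 0.05 per year and q = 0.1 in both arms it removes about 6%.

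**The case against.** The strongest reply is that the SAP already shows which text governs. The last column of the table is given the job of deciding exclusions, 7 presupposes IPVs that do not exclude, and the time-limited entries would have no function under 6.3. On that view 6.3 is loose wording, set membership is settled at the report planning or database lock meeting (blinded where possible), and a technical SAP and dataset plan that are not part of these documents may hold the detail. Most of this stands, and it is why the table should be kept and 6.3 corrected. It does not supply the missing censoring date in 7.4. SAP 6.2 and 6.3 also allow some IPV and set decisions after database lock in an open-label trial, so the rule is better written down.

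A reader might infer that the per-protocol hazard ratio would be biased against dabigatran by about 15%, or that the non-inferiority conclusion depends on the choice. The documents do not support that:
- The 0.3 / 0.1 split is an assumption. D3.1, which can arise only in the warfarin arm, lasts one month (bare metal stent) or three months (drug-eluting stent); D3.2 applies in every arm.
- Interrupting study drug after a bleed should mostly not create C3, because SAP 7.3 leaves interruption time out of capsule compliance and out of time in therapeutic range.
- The direction reverses if the imbalance does.

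Nor do the documents show that the 10% rule would turn on the wording. Patients excluded in full under either reading also count towards it, and the rule only permits skipping.

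**Conclusion.** The contradiction stands on the SAP's own text and needs no assumption: 6.3 as worded conflicts with 6.2 and Table 6.2:1, and the partial exclusions have no censoring date in 7.4. The reach is narrow. It covers the PPS analysis of the primary endpoint; the FAS primary analysis, all six hierarchical steps and the TS on-treatment analysis are unaffected.

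The size and direction of any bias cannot be found from the documents. The illustrations show only that literal use of 6.3 could matter if bleed-triggered violations were unbalanced: about 20 extra warfarin bleeds removed would carry an observed HR of 1.00 past the 1.38 margin. With balance, the ratio stays at about 1 and the cost is precision. These figures rest on the planned event numbers, a true or observed HR of 1, constant hazards and assumed violation rates. Concentration of bleeds in the early months would raise the one- and three-month figures. This should be corrected, but it is a consistency error in a supporting analysis.

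**What to change.** - **SAP 6.3:** replace the phrase requiring no IPV of any kind with: without any IPV that Table 6.2:1 marks as excluding the patient from the PPS in full.
- **SAP 7.4:** add that, for the PPS analysis, patients with C3, D3.1 or D3.2 are censored at the start of non-compliance and patients with B3 at withdrawal of consent. Say which recorded date counts as the start, given that C3 and D3 are judged by visit.
- **Table 6.2:1, A2.21:** reconcile the last column with the comment on pregnant patients.
- **10% rule in 6.3:** state whether partly excluded patients count. The text implies neither answer, so this is a choice to record.

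The cost is a few sentences and no new data. If the set has already been programmed, the report should say which rule was used.
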